# 6.2.2. Endpoint-Level Compliance

The daily eCOA assessments will be assigned a single four-weekly analysis time point as detailed within Section 6.3.4.2. Participants are considered compliant if the appropriate number of non-missing values for each interval per the criteria described in Section 6.3.4.2.

All visit-based eCOA assessments will be assigned analysis time points as detailed within Section 6.3.4.1. Participants are considered compliant if they complete the assessment at that visit.

The compliance for all eCOA endpoints in the multiplicity hierarchy (VRS, SNOT-22, ACQ-5) will be reported for each analysis time point by treatment group and total across treatment groups.

# 6.3. Appendix 3 Data Derivations Rule

# **6.3.1.** Criteria for Potential Clinical Importance

# 6.3.1.1. Laboratory Values

Haematology				
Laboratory Parameter	Units	Category	Clinical Concern Range	
			Low Flag (< x)	High Flag (>x)
Haematocrit	Ratio of 1	12+ years	0.201	0.599
Haemoglobin	G/L	12+ years	71	199
Platelet Count	x109/L	1+ years	31	1499
While Blood Cell Count (WBC)	x10  /L	12+ years	1.1	

Clinical Chemistry				
Laboratory Parameter	Units	Category	Clinical Concern Range	
			Low Flag (< x)	High Flag (>x)
Calcium	mmol/L	3+ years	1.50	3.24
Creatinine	IU/L	12+ years		>5 x ULN
Glucose	mmol/L	1+ years	2.2	27.8
Potassium	mEq/L	3+ years	2.8	6.5
Magnesium	mmol/L	6+years	0.3	2.5
Phosphorus	mmol/L	3+years	0.32	
Sodium	mEq/L	0+ years	120	160
ALT	U/L	12+ years		>239
Creatine Phosphokinase	IU/L	12+years		>5xULN

Liver Function				
Laboratory Parameter	Units Category Clinical Concern Range		Clinical Concern Range	
			High Flag (>x)	
ALT/SGPT	U/L	High	3 x ULN	
AST/SGOT	U/L	High	3 x ULN	
AlkPhos	U/L	High	3 x ULN	
T Bilirubin	µmol/L	High	1.5 x ULN	

## 6.3.2. Study Period

Assessments and events will be classified according to the time of occurrence relative to the study intervention period.

**Pre-treatment** is defined as time prior to the first dose of study intervention.

Assessment/Event Date ≤ Study Treatment Start Date

**On-treatment** is defined as time from first dose to last date plus 182 days.

Study Treatment Start Date < Assessment/Event Date ≤ Date of Last Dose of Study Treatment + 182 days

**Post-treatment** is defined as any time post on-intervention window, i.e. > last dose date plus 182 days.

Assessment/Event Date > Date of Last Dose of Study Treatment + 182 days

Assessments collected on the date of randomization, for which there is no time of assessment will be considered pre-intervention.

Assessments will be considered on-treatment if the assessment start date is missing.

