6.4. Study Intervention Compliance

- Participants will receive study treatment directly from the investigator or designee, under medical supervision. The date and time of each dose administered in the clinic will be recorded in the source documents. The dose of study treatment and study participant identification will be confirmed at the time of dosing by a member of the study site staff other than the person administering the study treatment.
- Participants will be monitored for a minimum of 2 hours (both at randomization and at Week 26) after study intervention administrations in the clinic. In the event of an acute severe reaction (e.g., anaphylaxis) following administration of study treatment, there are personnel/staff onsite at the treatment facility who are appropriately trained in basic life support to manage the participant including administration of medications (e.g., epinephrine), and have access to a system that can promptly transport the patient to another facility for additional care if appropriate.
- Administration will be documented in the source documents and reported in the eCRF.

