8.4.1. Time Period and Frequency for Collecting AE and SAE Information

- All SAEs will be collected from the start of intervention (Day 1) until the follow-up visit at the timepoints specified in Table 1. However, any SAEs assessed as related to study participation (e.g., study intervention, protocol-mandated procedures, invasive tests, or change in existing therapy) or related to a GSK product will be recorded from the time a participant consents to participate in the study.
- All SAEs will be recorded and reported to the sponsor or designee immediately and under no circumstance should this exceed 24 hours, as indicated in Appendix 3. The investigator will submit any updated SAE data to the sponsor within 24 hours of it being available.
- All AEs will be collected from the start of intervention (Day 1) until the follow-up visit at the timepoints specified in Table 1.
- Medical occurrences that begin before the start of study intervention but after obtaining informed consent will be recorded as medical history/current medical conditions not as AEs.
- Investigators are not obligated to actively seek information on AEs or SAEs after conclusion of the study participation. However, if the investigator learns of any SAE, including a death, at any time after a participant has been discharged from the study, and he/she considers the event to be reasonably related to the study intervention or study participation, the investigator must promptly notify the sponsor.

NOTE: The method of recording, evaluating and assessing causality of AEs and SAEs and procedures for completing and transmitting SAE reports to GSK are provided in Appendix 3.

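### The date formulas in SAP 6.3.2 class events on the first dosing day as pre-treatment, against the section's own wording, so those events drop out of the outputs labelled on-treatment

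*SAP*

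**What the plan says.** SAP 6.3.2 sorts both assessments and events into study periods, giving a description in words and a date formula for each period.

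- **Pre-treatment.** In words, it is the time before the first dose. The formula is "Assessment/Event Date ≤ Study Treatment Start Date".
- **On-treatment.** In words, it "is defined as time from first dose to last date plus 182 days". The formula is "Study Treatment Start Date < Assessment/Event Date ≤ Date of Last Dose of Study Treatment + 182 days".
- **Same-day default.** "Assessments collected on the date of randomization, for which there is no time of assessment will be considered pre-intervention". No equivalent rule is given for events.

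Protocol 8.4.1 fixes when AE collection begins: "All AEs will be collected from the start of intervention (Day 1) until the follow-up visit at the timepoints specified in Table 1". Occurrences between consent and the first dose "will be recorded as medical history/current medical conditions not as AEs". The exception is SAEs related to study participation or to a sponsor product, which are recorded from consent.

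SAP 6.3.6 replaces some partial AE start dates with the treatment start date. It does so when the known month and year (or the year alone, if the month is missing) match those of the treatment start, unless a full stop date falls before it.

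Three outputs carry an on-treatment label: the AE overview by Region 2 and the AEs by system organ class and preferred term by subgroup (both SAP 4.10.1.2), and the SAE row of the benefit-risk forest plot (SAP 4.9).

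**The concern.** The two halves of 6.3.2 classify the first dosing date in opposite ways, and it is the date on which an acute reaction to the first injection would be recorded. Protocol 6.4 states: "Participants will be monitored for a minimum of 2 hours (both at randomization and at Week 26) after study intervention administrations in the clinic". At Week 0, all of that observation falls on a date the formula calls pre-treatment. The same reaction after the Week 26 injection would be on-treatment.

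If the formula is programmed as printed, a first-dose-day event is missing from every output restricted to on-treatment events. A participant who receives only the first dose has no second dosing date on which a reaction could be counted. Protocol 7.1.1 makes this case relevant, since a severe allergic reaction with no clear alternative cause ends study treatment.

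The partial-date rule adds a second route. An AE whose start is imputed to the treatment start date becomes pre-treatment by formula, although the imputation has already set aside events known to have ended before dosing.

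**Working it through.** The plan states no figure to reproduce here. The check applies each version of the rule to event dates and compares the resulting classes.

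**Inputs**

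- Offset *d* = event date minus first dose date, so *d* = 0 is the first dosing day (Day 1).
- Second dose at *d* = 182 (26 weeks; SAP 4.5.1 counts each dose as 182 days of cover).
- On-treatment ends at last dose + 182 days (SAP 6.3.2).
- 125 randomised per arm, or 118 evaluable (SAP Section 5).

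**Step 1. Rules**

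- Formula: pre if *d* ≤ 0; on if 0 < *d* ≤ last dose + 182; post otherwise.
- Wording, for an event after the dose: pre if *d* < 0; on if 0 ≤ *d* ≤ last dose + 182; post otherwise.

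**Step 2. Classes, two doses**

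| *d* | Formula | Wording |
|---|---|---|
| -1 | pre | pre |
| 0 | **pre** | **on** |
| 1 | on | on |
| 182 | on | on |
| 183 | on | on |
| 364 | on | on |
| 365 | post | post |

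The only difference is at *d* = 0.

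**Step 3. Size of the window**

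- Two doses, wording: *d* = 0 to 364, which is 365 dates.
- Two doses, formula: *d* = 1 to 364, which is 364 dates. Of the dosing dates {0, 182} it keeps {182}, one of two.
- One dose, wording: *d* = 0 to 182, which is 183 dates.
- One dose, formula: *d* = 1 to 182, which is 182 dates. It keeps none of the one dosing date.

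**Step 4. Which version the other rules support**

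- Under Protocol 8.4.1 an AE dated Day 1 should be post-dose, apart from the SAE exception. This fits the wording.
- The default for untimed assessments on the randomisation date would have nothing to do if every record on that date were already pre-treatment.
- The partial-date imputation in SAP 6.3.6 moves uncertain AEs to the start date. Under the formula they all become pre-treatment, whereas 6.3.2 sends assessments with a missing start date to on-treatment.

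**Step 5. Effect of one affected participant**

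If a participant's only event in a table row is dated Day 1, the arm's percentage in that row falls by 1/125 = 0.80 points, or 1/118 = 0.85 points. This is before any split by subgroup.

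The documents give no Day 1 event rate, so the expected number of such participants cannot be computed. The nearest information is from the first-in-human study (Protocol 2.3.1): no allergic reactions on depemokimab, and injection-site reactions in one participant on active (1/36 = 2.8%) and one on placebo (1/12 = 8.3%), with no timing given.

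**The case against.** The strongest reply is that the intent is plain. The section speaks of time of occurrence and of time from the first dose, so this is a slip in an inequality that a competent programmer would resolve from the words above it. AE displays are also deferred to the sponsor's core data standards and to the Programming Specifications, which may already handle the date correctly. That is possible. But those documents are not available here, and a specification that follows the SAP formula would carry the error forward.

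The following points stand and limit the consequence:

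- The standard AE tables (SAP 4.5.2) and the special-interest tables (4.5.2.1) state no on-treatment restriction. Allergic and injection-site reactions have their own tables there, so an acute first-dose reaction would not vanish from the report.
- In the benefit-risk plot only the SAE row is labelled on-treatment. SAP 4.9 says its AE results come from 4.5.2.1, so even that row is less certain than the subgroup tables.
- Neither 125 nor 118 is the exact safety denominator, because the Safety set excludes two sites, and the tables in 4.10.1.2 are split further by subgroup. The 0.80 and 0.85 points are a scale, not an estimate.
- For the Visit 2 assessments that the protocol requires before dosing, including the first dosing date in pre-treatment gives the right class. The problem is with events.
- No passage says that AE onset time is collected.

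A PDF reading error is unlikely. The two signs are distinct and complementary, so conversion would have had to add a bar in one formula and drop it in the other.

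**Conclusion.** SAP 6.3.2 contradicts itself for the first dosing date and, applied as printed, its formulas misclassify AEs that occur after the first injection on that day. The textual conflict is certain. Its effect is one calendar date per participant: one of two dosing dates is lost, or the only one for a participant with a single dose. The outputs exposed are the on-treatment AE tables by subgroup and, less certainly, the on-treatment SAE row of the benefit-risk plot. Efficacy, data collection and, on the text available, the main AE and special-interest tables are not affected.

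This rests on three assumptions: the formulas are programmed as printed; the first dose is given on the randomisation date, as the Schedule of Activities plans; and Day 1 AEs follow the dose, as Protocol 8.4.1 implies apart from the SAE exception. The number of events lost is unknown. The point should be fixed, because otherwise two programmers could follow the same section and report different safety counts.

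**What to change.** In SAP 6.3.2, separate the rule for AEs from the rule for assessments, before unblinding.

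- **AEs, pre-treatment:** event date < treatment start date.
- **AEs, on-treatment:** treatment start date ≤ event date ≤ last dose date + 182 days. Say explicitly that this includes AEs whose partial start date is imputed to the treatment start date under 6.3.6.
- **Timed Day 1 events:** where an onset time is recorded, class an event before the dose as pre-treatment. Dose time is available: "The date and time of each dose administered in the clinic will be recorded in the source documents".
- **Scheduled assessments:** keep the default that an untimed record on the randomisation date is pre-intervention, and limit it to these.

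No date other than the first dosing day changes class. The cost is SAP wording and one flag derivation. The residual risk is that an untimed Day 1 SAE that in fact preceded the dose is counted as on-treatment, which is the conservative direction for safety.

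As a separate housekeeping check that carries no weight in this conclusion, compare the signs in SAP 6.1.4 with the source file. As printed, post-treatment medications are those starting before last dose + 182 days, and a medication starting on the treatment start date meets neither the pre-treatment nor the on-treatment rule.

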# 6.3.3. Study Day and Reference Dates

The safety reference date is the study intervention start date and will be used to calculate study day for safety measures.

The efficacy reference date is the date of randomization and will be used to calculate study day for efficacy measures and baseline characteristics, as well as efficacy durations.

The study day is calculated as below:

- Assessment Date = Missing  $\rightarrow$  Study Day = Missing
- Assessment Date < Reference Date → Study Day = Assessment Date Ref Date

- Assessment Data  $\geq$  Reference Date  $\rightarrow$  Study Day = Assessment Date Ref Date + 1

#### 6.3.4. Assessment Window

#### 6.3.4.1. Visit Based Assessments

No assessment windows are defined for visit based assessments. Nominal visits will be used for all reporting and analysis. Further details on the mapping of unscheduled visits are provided in the Programming Specifications document.

#### **6.3.4.2.** Daily Diary

Participants are to complete a daily diary assessment each morning. Table 2 below displays which daily diary records are included for each analysis time period. Any daily diary data collected post the 52-week time period will not be included in the Weeks 49-52 analysis of diary data.

Table 2 Daily Diary Assessment Windows

Analysis for AM Measures		
Beginning Timepoint (Day)	Ending Timepoint (Day)	Analysis Time Period
-27	1	Baseline
2	29	Weeks 1 – 4
30	57	Weeks 5 – 8
58	85	Weeks 9 – 12
86	113	Week 13 – 16
114	141	Weeks 17 – 20
142	169	Weeks 21 – 24
170	197	Weeks 25 – 28
198	225	Weeks 29 – 32
226	253	Weeks 33 – 36
254	281	Weeks 37 – 40
282	309	Weeks 41 – 44
310	337	Weeks 45 – 48
338	365	Weeks 49 – 52

Note: There is no Day 0 in CDISC reporting. Days -27 to -1 are immediately pre-randomization and Day 1 is the day of randomization (Visit 2). For the baseline time period, all values from Day -27 to Day 1 will be included in the baseline average; however, there must be a minimum of 4 non-missing values from Day -6 to Day 1 inclusive in order to derive the baseline, otherwise it will be set to missing.

Note: For each 4-week post-baseline time period the average will only be derived if there are non-missing values for at least 4 days out of 7 in at least 3 out of 4 weeks, with at least 15 minimum values, otherwise it will be set to missing.

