CT Scan	X															X	X		CT scan is mandatory unless not approved by local ethics committee or institutional review board. The first CT scan must be performed prior to randomization and should be the last assessment performed, where possible. If the first CT scan cannot be performed as the last assessment before randomization, the subject should have completed their screening visit and all screening lab results, the central NP score and ECG central over-read results should be assessed by the PI before a CT scan is conducted. The second CT scan should be performed at V16 or EW visit (up to 14 days prior to the nominal study visit). Note: If a participant is permanently discontinued both from the study intervention and from the

26 Jun 2024 36

																		1 10	olocoi Amendineni 5 Finai
	Screening (Visit 1) ^{a, d}						Trea	tmer	nt Pe	riod	I						Withdraw/I	Follow Up	
Procedure	Visit							We	ek								EW Visit	Follow-up	Notes
) Bı	0	4	8	12	16	20	24	26	28	32	36	40	44	48	52		30/56	
	enii								\	/isit	(±7	day	s)						
	Scre	2a	3a	4 c	5a	6b	7 a	8b						14	b 15	16	a, e	b, e	
																			study, and the second dose of study intervention was not received, decision on performing CT scan during EW visit at Week 26 will be made by the investigator in consultation with the Medical Monitor. Please refer to Pregnancy test (WOCBP only)
Assessment of Actual NP Surgery or planned NP Surgery		X	х	х	х	Х	х	х	х	х	х	х	Х	х	х	х	Х		Wherever possible (and when optional consent provided for exploratory biomarkers), the removed tissue from a nasal surgery will be collected and stored. Not applicable for China.
Assessment of systemic CS and antibiotics dose and duration including for CRSwNP		Х	Х	х	Х	Х	х	Х	х	Х	Х	Х	Х	Х	Х	Х	Х	Х	

218079

	T																	ГІС	Diocoi Amendment 5 Finai
	Screening (Visit 1) ^{a, d}					•	Treat	tmen	t Pe	riod							Withdraw/F	Follow Up	
Procedure	/isit							We	ek								FW Visit	Follow-up	Notes
Toocaare) 6 1	0	4	8	12	16	20	24	-	28	32	36	40	44	48	52	26 or 52	30/56	110103
	enir								V	/isit	(+7 (days)					•	
	Scree	2a	3a	4 c	5a	6 ^b	7a	8 b	9a					14b	15ª	16a	a, e	b, e	
Patient-Reported Outcomes		_					•											l	
Dispensing and Training of the eDiary	Х																		
eDiary Compliance Check		Х	Х	Х	Χ	Χ	Χ	Χ	Χ	Χ	Χ	Χ	Χ	Х	Χ	Χ	Х		
eDiary Collection																Χ	Х		

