Individual symptom scores (including nasal obstruction, rhinorrhea [runny nose], loss of smell, facial pain, and mucus in throat) (VRS) ^f	Х	Х	х	Х	Х	Х	х	X	Х	Х	Х	Х	Х	Х	Х	Х	Х		Performed using eDiary. eDiary will be completed by participants in the morning between Screening Visit (V1) and V16.
Overall symptoms score (VAS)f	Х	X	х	Х	х	Х	х	Χ	X	Х	Х	Х	Χ	Х	Х	X	X		Performed using eDiary. eDiary will be completed by participants in the morning between Screening Visit (V1) and V16.
Nasal obstruction score (VAS)f	Х	Х						Χ								Χ	Х		Performed using eDiary.
SNOT-22 ^f		Χ	Χ	Χ	Χ	Χ	Χ	Χ	Χ	Χ	Χ	Χ	Χ	Χ	Χ	Χ	Χ		Performed using eDiary.
PGISf		X	х	Х	х			Х					Χ			Χ	Х		Performed using eDiary. The PGIS will ask the patient to rate the severity of their nasal polyps symptoms over the last 4 weeks.
PGIC ^f ACQ-5 ^f		X	х	X	х	X		X	X		X		X		X	X	X		Performed using eDiary. The PGIC will ask the patient to rate the change in their nasal symptoms since the start of trial medication. For asthmatic participants
ハレベ- リ		^		_ ^		_ ^		^	^		_ ^		^		_ ^	Λ	^		i oi astiillatic participalits

																		ГІС	Diocoi Amendment 5 Finai
	Screening (Visit 1) ^{a, d}					7	Trea	tmen	nt Pe	riod							Withdraw/F	ollow Up	
Procedure	Visit							We	ek								EW Visit	Follow-up	Notes
) Br	0	4	8	12	16	20	_	-	28	32	36	40	44	48	52	26 or 52	30/56	
	enir								\	/isit	(±7 (davs	5)						
	Scre	2a	3a	4 c	5a	6b	7a	8b	9a					14b	15a	16a	a, e	b, e	
																			only. Performed using eDiary.
Review for asthma exacerbations		X	X	X	X	X	X	X	X	x	X	X	X	х	X	X	Х	X	For asthmatic participants only. An asthma exacerbation is defined as worsening of asthma requiring systemic corticosteroids (IV or oral steroid) for at least 3 days or a single IM CS dose and/or emergency department visit, or hospitalization.
SF-36 ^f		Χ		Χ					Χ				Χ			Χ	Х		Performed using eDiary.
WPAI-GH ^f		Χ		Х					Χ				Х			Χ	Х		Performed using eDiary.
Laboratory Assessments																			
Parasitic screening	X																		Parasitic screening is only required in countries with highrisk or for participants who have visited high-risk countries in the past 6 months. Please refer to SRM for full list of high-risk countries. Sites should use local laboratories. If sites wish to use central laboratories, they should note that the central test is stool microscopy for ova and parasites. For details of the organisms detected by this test

	Screening (Visit 1) ^{a, d}					1	Гrea	tmen	ıt Pe	riod							Withdraw/l		DOCOL AMENGMENT 3 FINAL

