8.2. Efficacy Assessments

8.2.1. Endoscopic NP Score

Endoscopic NP score will be assessed at study visits as described in Table 1. This score is graded based on NP size and recorded as the sum of the right and left nostril scores with a range of 0-8; higher scores indicate worse status.

Endoscopic NP score will be performed at the site by trained health care professional (usually ENT surgeon). All image recordings of endoscopies will be sent to an independent reviewer at Clario, the central lab for blinded NP scoring. There is potential for the site score to differ from the central score. In such cases, the output from the central labs is considered final and will be utilized for patient eligibility and for the analysis of this endpoint (for additional details refer to the Clario Video Guideline).

For Visit 2, the nasal endoscopy assessment may be performed up to 7 days prior to the clinic visit but must occur prior to randomization. For all other visits the nasal endoscopy assessment must not exceed the protocol defined windows of ± 7 days from the nominal study visit.

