### 4.2. Primary Endpoints Analyses

### 4.2.1. Definition of endpoints

The co-primary endpoints are:

- a) Change from baseline in total endoscopic NP score at Week 52 (centrally read)
- b) Change from baseline in mean nasal obstruction score (verbal response scale [VRS]) from Week 49 through to Week 52

The total endoscopic NP score is assessed in the clinic at visits 2, 5, 7, 9, 11, 13, 15 and 16, or early withdrawal visit (weeks 0, 12, 20, 26, 32, 40, 48 and 52). The score is then graded by independent reviewers at a central lab who are blinded to treatment. The total score is reported as the sum of the right and left nostril scores and ranges from 0 to 8, with higher scores indicating greater disease severity. Non-missing scores must be available for both sides for the combined score to be calculated; otherwise the score will be set to a value of 9 to indicate a missing or unreadable value.

The nasal obstruction VRS score will be collected daily in the morning via the eDiary. Each day the participant will indicate the severity of their symptoms giving a score ranging from 0 to 3, with the 4 options indicating no symptoms, mild symptoms, moderate symptoms, and severe symptoms. The daily data will be collapsed into thirteen 4-week time periods, with the value for each time period based on the average of the non-missing days covered by that time period as described in Section 6.3.4.2. For each 4-week time period the average will only be derived if there are non-missing values for at least 4 days out of 7 in at least 3 out of 4 weeks, with at least 15 minimum values, otherwise it will be set to missing.

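### The Weeks 49–52 diary period is fixed at Days 338–365 but diary entry ends at V16, so a V16 on Days 358–361 removes the completeness rule's allowance for one poor week

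*SAP*

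**What the plan says.** SAP 6.3.4.2 (Table 2) assigns diary days to periods by study day alone. The last row reads "338 365 Weeks 49 – 52". A note deals with late data: "Any daily diary data collected post the 52-week time period will not be included in the Weeks 49-52 analysis of diary data". A period mean needs "non-missing values for at least 4 days out of 7 in at least 3 out of 4 weeks, with at least 15 minimum values"; a period that fails this is missing. SAP 4.2.1 repeats the rule for the co-primary endpoint.

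The Schedule of Activities (Protocol 1.3) ends entry at the last treatment visit: "eDiary will be completed by participants in the morning between Screening Visit (V1) and V16". Its row for "eDiary Collection" is marked at V16 and the early withdrawal visit. The table header gives every visit a ±7-day window, and Protocol 8.2.1 also refers to "protocol defined windows of ± 7 days".

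Neither document says what happens to the final period when V16 is early, and the SAP does not define the weeks inside a 4-week period.

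**The concern.** For every earlier period the diary runs on past the visit, so visit timing does not matter. The last period is different: entry stops at V16 while the window stays open to Day 365. An early V16 can therefore take up to 7 days from the period that defines one co-primary endpoint and two VRS secondary endpoints (rhinorrhoea and loss of smell).

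The completeness rule is not adjusted for this, so the same diary habits can give a value or a missing value depending on the clinic date. The MMRM treats the gap as missing at random. In the responder analyses, however, SAP 4.4.1 counts a missing post-baseline timepoint as non-response. SAP 4.4.2 reports odds ratios with p-values for the nasal obstruction, loss of smell and rhinorrhoea responder endpoints.

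**Working it through.** **The plan's own figures.** SAP section 5 gives a difference of -0.70, SD 0.84, two-sided 5% and 118 evaluable per arm.
- Standard error = 0.84 × √(2/118) = 0.1094.
- Power = Φ(0.70/0.1094 − 1.96) > 99.99%; the plan states >99%.
- Smallest significant difference = 1.96 × 0.1094 = 0.214; the plan states -0.21.

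Both reproduce.

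**The window.** Randomisation is Day 1 (SAP 6.3.3), so Week 52 is Day 1 + 364 = Day 365 and the earliest V16 is Day 358. Period 13 starts on Day 2 + 28 × 12 = 338 and ends on Day 365, as in Table 2. I take the weeks as consecutive 7-day blocks: Days 338–344, 345–351, 352–358 and 359–365. This is an assumption. The V16 morning entry counts, because the Schedule of Activities puts questionnaires before other assessments.

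**The rule under an early V16.** The fourth week has V16 day − 358 available days, so 0 to 3 for V16 on Days 358–361. It cannot reach 4, and all of the first three weeks must.

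| Entries, V16 on Day 358 | Result | Same habits, V16 on Day 365 | Result |
|---|---|---|---|
| 7+7+7 = 21 | derived | 7+7+7+7 = 28 | derived |
| 5+5+5 = 15 | derived | 5+5+5+5 = 20 | derived |
| 7+7+3 = 17 | missing (2 qualifying weeks) | 7+7+3+7 = 24 | derived |
| 5+5+4 = 14 | missing (<15) | 5+5+4+5 = 19 | derived |
| 4+4+4 = 12 | missing (<15) | 4+4+4+4 = 16 | derived |

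On Day 358 the largest failing total is 17 of 21 (81%), so 18 or more always passes. The 4-per-week pattern gives 12, 13 and 14 values for V16 on Days 358, 359 and 360 (missing) and 15 on Day 361 (derived).

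**Probability of a missing value.** This is an exact enumeration of weekly counts. Each week is binomial with its available days and daily completion p, days are independent, and the rule is at least 4 entries in at least 3 weeks and at least 15 in total.

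| p | Day 358 | Day 361 | Day 362 | Day 365 |
|---|---|---|---|---|
| 0.70 | 50.0% | 35.4% | 27.4% | 8.2% |
| 0.80 | 15.0% | 9.9% | 5.9% | 0.6% |
| 0.85 | 5.1% | 3.6% | 1.7% | 0.1% |
| 0.90 | 1.0% | 0.8% | 0.3% | <0.1% |

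**Study level.** The documents give no distribution of V16 dates. If V16 is assumed uniform over Days 358–372 (15 days, with Days 365–372 all giving the Day 365 risk), the average at p = 0.80 is (0.1497 + 0.1172 + 0.1038 + 0.0989 + 0.0592 + 0.0281 + 0.0126 + 8 × 0.0064)/15 = 4.1%. The same sum gives 1.3% at 0.85, 0.3% at 0.90 and 19% at 0.70. Of that 19%, about 8 points arise without any early visit.

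**Effect on power.** If 20% of values were lost in both arms (94 per arm), power is 99.99%. At 30% (82 per arm) it is 99.96%.

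**The case against.** The strongest reply is that the rule already tolerates one lost week, which is the most an early V16 can remove. A participant who fills in the diary every morning, as instructed, has 21 values and passes. That stands: with V16 on Days 358–361, only someone who misses at least 4 of the available mornings can fail.

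A reader might infer that participants who comply with the protocol lose their co-primary value. The documents do not support that. The 4-of-7 threshold in Protocol 5.3 is a randomisation criterion covering only the week before Visit 2, and SAP 6.2.2 defines endpoint-level compliance as meeting the completeness rule itself. A reader might also take 8% versus 50% as the size of the problem. That combines the earliest permitted V16 with 70% completion, which in SAP 6.2.1 is a target pooled over all electronic assessments and participants, not a final-month diary rate.

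It can also be said that Protocol 8.2.2.1 collects the VRS to the end of the Treatment Period, so entry might continue to Day 365. But the Schedule of Activities closes that period at V16 and takes the device back there. The COVID-19 appendix (10.11.5) allows return by mail after a Visit 17 that the Schedule does not contain. At best the end of diary entry is ambiguous.

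Finally, the MMRM keeps the participant's earlier 4-week periods, and missingness caused by scheduling in a double-blind trial fits MAR well. I accept this for the co-primary analysis; nothing in the documents points to a bias between arms. It does not help the responder analyses, although those are endpoints in the Other category without multiplicity adjustment. The tipping-point analysis in SAP 4.2.3 is worded around study withdrawal and does not clearly cover these gaps.

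**Conclusion.** The plan creates avoidable missing values in the final VRS period, and visit scheduling is what triggers them. The mechanism follows from the two documents read together and needs no assumption beyond weeks being consecutive 7-day blocks. Its size does rest on assumptions. With independent days and V16 on Day 358, the added risk is about 14 percentage points at 80% completion (15.0% − 0.6%) and 5 points at 85% (5.1% − 0.1%). The study-level loss cannot be computed from the documents. Under the uniform V16 assumption it is about 4% at 80% and 1% at 85%.

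This is not a threat to the stated power or a demonstrated bias in the co-primary comparison. It is a gap worth closing because it falls on a co-primary window, turns some participants into non-responders by rule, and is easily prevented.

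**What to change.** In the Schedule of Activities, have any participant whose V16 falls before Day 365 keep the eDiary and continue daily entry through the Day 365 morning. The V16 window and SAP Table 2 stay as they are. The cost is a protocol amendment and a device returned up to 7 days later. Moving the V16 window to Day 365 or later would also protect the diary, but it would shift endoscopy, CT and safety assessments as well, so I would not choose it.

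For participants already seen early, state in SAP 6.3.4.2, before unblinding, how the final period is derived. If it is the 28 days ending at V16, a Day 358 visit would use Days 331–358, which overlaps Weeks 45–48 (Days 310–337) by 7 days. The SAP must then say how the shared entries are handled in the MMRM, for example by confining that derivation to a sensitivity analysis. The same note should define the weeks within each 4-week period.
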